Fixed-Dose Netupitant and Palonosetron for Chronic Nausea and Vomiting in Cancer Patients

Principal Investigator: [name]
Co-Principal Investigator: [name]
Collaborators: [name], [name], [name], [name]
[name], [name], [name], [name], [name]
[name]
Biostatistics Collaborators: [name], [name]

Table of Contents

A. Study Objectives	2
B. Background	2
C. Pharmaceutical Information	5
D. Experimental Approach	7
E. Patient Withdrawal Criteria	13
F. Investigator Communications with Helsinn	
G. Serious Adverse Events Reporting	16
H. Statistical Considerations	17
I. Data Confidentiality Procedures	
J. References	

A. Study Objectives

Primary objective:

To estimate the efficacy (i.e. change in nausea numeric rating scale [NRS] from baseline between day 5-15) of fixed dose netupitant and palonosetron (NEPA) for chronic nausea in cancer patients.

Secondary objective:

- 1. To assess the secondary outcomes (e.g. proportion of patients who achieved their personalized nausea goal, antiemetic use, nausea episodes duration/frequency) for NEPA vs. placebo.
- 2. To assess the adverse effects associated with NEPA and placebo.

B. Background

B.1. Significance of Chronic Nausea in Cancer Patients. Nausea is defined as "an unpleasant sensory and emotional experience, which may be described in terms of a sick feeling with or without a sense of impending vomiting/retching - often associated with a perception of epigastric or upper abdominal unpleasantness or awareness".¹ Chronic nausea is defined as nausea of 1 month or greater.^{2,3} In one systematic review of 39 studies consisting of 24263 patients with incurable cancer, nausea occurred in 31% (95% confidence interval [CI] 27-35%) of patients, and vomiting in 20% (95% CI 17-22%).⁴ In another systematic review of far advanced cancer patients, the prevalence of nausea was estimated to be 6-68%.⁵ Rhondali et al. reported that among 444 cancer patients seen at the supportive care clinic at MD Anderson Cancer Center, 112 patients had moderate/severe chronic nausea of >=4/10 in intensity.⁶ 68/112 (61%) patients had a response (defined as 30% improvement from baseline) to the multimodal therapies offered by the palliative care team (e.g. metoclopramide, ondansetron, other anti-emetics, constipation management, counseling) at the followup visit 2 weeks later.

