D.1. Study Design. This is an investigator-initiated study supported by Helsinn. We propose a 2-arm, double blind, placebo run-in, parallel randomized controlled trial of NEPA vs. placebo for cancer patients with chronic nausea and vomiting, to be followed by an open label extension phase (Figure 1). This is a proof-ofconcept study enrolling 30 evaluable patients. The main goal of this study is to determine the effect size for both NEPA and placebo arm in order to inform a larger, adequately powered confirmatory randomized controlled trial.

After study consent, eligible patients will be asked to try a single dose of study medication (placebo) over a 5 +/-2 day period, in a single-blinded fashion. Those without a significant

placebo response by Day 5 +/-2 will then be randomized to NEPA or placebo for 10 days. Study drug will be mailed to study participants. We will also offer an optional open label extension for 10 more days after the blinded phase so patients may receive NEPA for nausea control if desired. Patients will complete assessments similar to the blinded phase (Table 4). We believe this study design is feasible and would not add undue burden for patients. Patients will be compensated with a \$50 gift card for their time and effort. Patients may also be reimbursed for parking charges for study visits at a total of up to \$45 for all study visits.

2016-0843 Rev. August 22, 2018 Page 8 of 22

The placebo run-in period will allow us to (1) evaluate patients prior to exposure to the experimental treatment, (2) exclude patients who develop a significant placebo response given that our primary outcome is subjective, and (3) select patients who have a higher chance of completing the study. This design has been used in multiple other supportive care randomized trials without affecting their internal validity.³³⁻³⁵ The use of rescue medications will be allowed (metoclopramide 10 mg q4h PRN for breakthrough nausea).

D.2. Eligibility Criteria. The eligibility criteria are shown in Table 2. **Table 2. Study Eligibility Criteria**

Inclusion Criteria

- 1. Diagnosis of cancer
- 2. Chronic nausea over the past 4 weeks
- 3. Average nausea numeric rating scale $\geq 4/10$ over the past 5 days at screening
- 4. Outpatient at MD Anderson Cancer Center
- 5. Karnofsky performance status >/=50%
- 6. Age 18 or older
- 7. Able to complete study assessments, including keeping a daily diary

Exclusion Criteria

- 1. Delirium (i.e. Memorial Delirium Rating Scale >13)

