- Functional Living Index Emesis (FLIE)—a questionnaire validated to assesses the impact of chemotherapy-induced nausea and vomiting on patient's function and quality of life over the past 5-days. It consists of 18 items, with 9 items on nausea and 9 items on vomiting. The questions include how much nausea/vomiting, and impact of these symptoms on recreation or leisure activities, make meal/do tasks, ability to enjoy meal, enjoy drinking fluids, see family/ friends, daily functioning, personal hardship, and hardship on others. Each question was rated using a numeric rating scale from 1-7. The total score range from 18 to 126, where a higher score indicates higher quality of life.⁴³⁻⁴⁶

D.11 Feasibility data. In addition to clinical outcomes, we will also collect feasibility data in this study, including the following:

- Rates of recruitment and retention (% of subjects able to complete the study)
- Reasons for refusal and dropout
- Participant satisfaction—participants will provide an opinion regarding their satisfaction with study overall

D.12. Patient Safety, Monitoring, and Confidentiality. Regulatory monitoring will be provided by the principal investigator, Institutional Review Board (IRB), and the Data Safety Monitoring Board (DSMB). Patient confidentiality will be ensured by use of study numbers, secure storage of clinical data, and anonymous reporting.

Table 4. Summary of Study Assessments							
Assessments	Day of enrollment	Days 1-25	Day 5±2	Day 10±2	Day 15±2	Days 20±2 25±2 ¹	
Screening procedures (eligibility criteria)/ Pregnancy Test/Calculated creatinine clearance, T. bilirubin, albumin, prothrombin time, serum creatinine	✓ Pregnancy test within 7 days of						

					5	-
	signing consent					
	CONSEIN					
Baseline characteristics ² (Appendix A)	✓					
Medication history ³ (Appendix A)	✓					
Nausea Diary including nausea numeric		\checkmark^{\star}				
rating scale (primary outcome), rescue						
medications and Index of nausea and						
vomiting and retching ⁴ (Appendix B)						
Edmonton Symptom Assessment Scale ⁵	\checkmark			√*	√*	√*
(Appendix C)						
Personalized nausea goal ⁶ (Appendix D)	\checkmark				√*	
Functional Living Index Emesis ⁷ (Appendix	✓			√*	√*	√*
E)						
Global assessment (Appendix F), study					√*	
satisfaction (Appendix H) and blinding						
(Appendix G) ⁸						
Nausea Numeric Rating Scale past 5 days	\checkmark		√*	√*	√*	√*
(Appendix U) ⁹						

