- Additionally, any serious adverse events that occur after the 30 day time period that are related to the study treatment must be reported to the IND Office. This may include the development of a secondary malignancy.

Reporting to FDA:

• Serious adverse events will be forwarded to FDA by the IND Sponsor (Safety Project Manager IND Office) according to 21 CFR 312.32.

It is the responsibility of the PI and the research team to ensure serious adverse events are reported according to the Code of Federal Regulations, Good Clinical Practices, the protocol guidelines, the sponsor's guidelines, and Institutional Review Board policy.

H. Statistical Considerations

The primary objective of this phase II study is to estimate the effect of NEPA on the nausea numeric rating scale (i.e. change between day 5 and day 15). The target accrual is 30 evaluable patients who complete the study with a randomization ratio of 2:1 (NEPA vs Placebo), but accrual will range from 41-50, given an attrition rate of 30-40%. With 20 patients in the NEPA arm, we would have a 92% power to detect a difference of 2 points with a standard deviation of 2.5 (effect size of 0.8) using two-sided paired t-test with a significance level of 0.05.

Descriptive statistics, including mean, standard deviation, 95% confidence intervals, median, range, frequency and percentage will be summarized for all variables of interest such as patients' demographics, clinical characteristics, personalized nausea goal, NRS and adverse effects, whichever appropriate.

We will focus on estimating the magnitude of change in NRS between day 5 and day 15. We will use a mixed model to examine the change in nausea overtime in both the NEPA arm and placebo arm.

We will estimate the proportion (with 95% confidence interval) of patients who achieve their personalized nausea goal for NEPA and placebo as a secondary outcome. Adverse effects associated with NEPA and placebo will be collected and frequency will be summarized.

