A comparison between NEPA and placebo is not the objective of this study. However, Chi-squared test or Fisher's exact test, whichever the most appropriate, will be used to test for association between categorical variables, such as CTCAE adverse effects, global assessment, and blinding. Wilcoxon rank sum test or Kruskal-Wallis test will be used to test for difference of continuous variables, such as ESAS and FLIE. General linear model may be considered to examine the effect of potential important factors on NRS.

A Response/Toxicity Summary will be submitted to the IND Office Medical Monitor, after the first ten evaluable patients complete study treatment, and every 10 evaluable patients thereafter.

I. Data Confidentiality Procedures

This study will be monitored by the MD Anderson IND Office and a protocol-specific monitoring plan will be followed.

All records identifying the subject will be kept confidential and, to the extent permitted by the applicable laws and/or regulations, will not be made publicly available.

During the study, trained research staff will be performing study assessments and monitoring the patient carefully throughout the study period. Regulatory monitoring will be provided by the principal investigator and the IND office. Patient confidentiality will be maintained by use of unique study numbers, secure storage of clinical data, and anonymous reporting.

Collection of identifiers: We will collect and securely store patients' identifiers (including name and medical record number). Each patient will be assigned a study number that will be the only identifier to figure in the analytical file and personal data will not be disclosed in any form. The key linking these numbers will be retained in a securely locked file by the investigator.

Data Storage: Protection of electronic and paper records will be maintained to the best of our ability. All electronic records will be stored on password-protected institution computers behind the institution firewall. Any paper records will be classified and stored in locked files inside a locked office.

Training of personnel: Only MDACC personnel trained in maintaining confidentiality, the principal investigators, co-investigators, and the research team will have access to study records.

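### The planned between-arm rank test for ESAS and FLIE names no baseline adjustment and no NEPA-minus-placebo estimate, although both scores are collected at enrolment

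*Combined protocol and SAP*

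**What the plan says.** Section H gives one sentence on testing these outcomes: "Wilcoxon rank sum test or Kruskal-Wallis test will be used to test for difference of continuous variables, such as ESAS and FLIE". It follows a disclaimer, "A comparison between NEPA and placebo is not the objective of this study", but the next word is however, and tests of difference are then planned. Section A, secondary objective 1, asks for secondary outcomes, among them "antiemetic use, nausea episodes duration/frequency) for NEPA vs. placebo".

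In D.12, "Table 4. Summary of Study Assessments" has a row for the "Edmonton Symptom Assessment Scale" and a row for the "Functional Living Index Emesis". Both are ticked on the day of enrolment, at days 10 and 15, and in the optional extension. Neither is ticked at day 5. The enrolment score therefore comes before the run-in, in which (D.1) "eligible patients will be asked to try a single dose of study medication (placebo) over a 5 +/-2 day period, in a single-blinded fashion".

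The other models in Section H concern nausea: a mixed model for nausea over time, and an optional general linear model for the NRS. Section H also plans descriptive statistics, including means and 95% confidence intervals, for all variables of interest. On size it says "The target accrual is 30 evaluable patients who complete the study with a randomization ratio of 2:1 (NEPA vs Placebo"), that is, 20 and 10 patients.

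**The concern.** With 10 patients in one arm and 20 in the other, chance differences in starting scores are often large. A two-sample rank test on final scores leaves them in the result. It also leaves unused whatever part of the outcome's variation the starting score explains.

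A rank test by itself gives a p-value. D.1 says the study is meant to supply effect sizes for planning a larger trial, and for that purpose an estimated difference with an interval is worth more. Because the plan does not fix the day or say whether final or change scores are tested, those choices also stay open until the data are in hand.

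**Working it through.** **The plan's own power figure.** Section H states 92% power for a two-sided paired t-test with n = 20, difference 2, SD 2.5 and alpha 0.05. The noncentral t with 19 df and noncentrality (2/2.5) × √20 = 3.58 gives 92.4%, so the figure reproduces. It concerns the within-arm change in nausea NRS in the NEPA arm and says nothing about ESAS or FLIE, for which the documents state no power, SD, effect or correlation.

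**Inputs.** From the documents: 20 versus 10 patients (Section H). Two-sided alpha 0.05 is carried over from the NRS calculation. Assumed: between-arm difference d = 0.8 SD, correlation rho of 0.2 to 0.7 between enrolment and final score, and normal scores.

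**Chance imbalance at baseline.** The standard error of the baseline difference is √(1/20 + 1/10) = 0.39 SD. A gap above 0.5 SD in either direction has z = 0.5/0.387 = 1.29, hence a probability of about 20% for each outcome. At rho = 0.5, a gap of 0.5 SD moves the final-score comparison by 0.5 × 0.5 = 0.25 SD.

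**Precision.** Adjustment multiplies the residual variance by 1 − rho². The 95% half-width is t(0.975, 27 df) × 0.387 × √(1 − rho²):

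| rho | Variance removed (rho²) | Half-width (SD) |
|---|---|---|
| 0 | 0% | 0.79 |
| 0.3 | 9% | 0.76 |
| 0.5 | 25% | 0.69 |
| 0.7 | 49% | 0.57 |

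At rho = 0.5 the gain equals having 30/(1 − 0.25) = 40 patients in place of 30.

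**Power.** Simulation with 4,000 runs per setting and d = 0.8. Share lost = 1 − (rank test on final score)/(ANCOVA), from unrounded powers:

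| rho | Rank test, final score | Rank test, change score | ANCOVA | Share lost, final score |
|---|---|---|---|---|
| 0.2 | 47% | 31% | 52% | 10% |
| 0.3 | 48% | 35% | 54% | 11% |
| 0.5 | 47% | 47% | 62% | 25% |
| 0.6 | 46% | 55% | 67% | 31% |
| 0.7 | 47% | 68% | 77% | 39% |

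At rho = 0.5 the share lost is about 25% for d = 0.5 (21% against 29%) and 18% for d = 1.0 (65% against 80%). A separate simulation at d = 0.8 gave 47% against 54%, 48% against 63% and 46% against 79% at rho 0.3, 0.5 and 0.7, so the share lost at 0.7 is about 40%. These models contain arm and baseline only; adding the stratum costs one further degree of freedom.

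**Departure from normality.** On an assumed 0–10 integer scale with a floor, the rank test against ANCOVA gave 44% against 55% at rho 0.5, and 43–44% against 47–48% at rho 0.2–0.3. With lognormal scores the figures were 46% against 49% at rho 0.5. At rho 0.2–0.3 the rank test did slightly better, 46–47% against 43–44%. Under stronger skew plain ANCOVA can also lose at rho 0.5. ANCOVA on ranks beat the unadjusted rank test in every setting tried.

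**The case against.** The strongest reply is that Section H disclaims the between-arm comparison, and that D.1 describes a proof-of-concept study. ESAS is not among the secondary endpoints listed in D.10, and neither score is among the examples in secondary objective 1. Power is modest with either method. This stands as a limit on importance. It does not dispose of the point, because the same paragraph goes on to plan these tests.

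A rank test is also a defensible choice for bounded ratings. Part of its shortfall on normal data has nothing to do with baseline: at rho = 0.5 the powers are 47% for the rank test, 52% for an unadjusted t-test and 62% for ANCOVA, so 5 of the 15 points come from the use of ranks. This stands too, and is why the fix includes a rank-based adjusted analysis.

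A reader might infer four stronger things that the documents do not support:

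- **That a fixed quarter of the power is lost.** This needs rho near 0.5, which the documents do not give. The starting score precedes the run-in and is about 15 days older than the day 15 score, so rho could be lower.
- **That no effect estimate will exist.** The descriptive statistics in Section H allow means and 95% CIs for each arm. Only a stated between-arm difference is missing.
- **That baseline is excluded.** The plan is silent on final versus change scores. A rank test on change would use the baseline, though less efficiently than ANCOVA.
- **That vomiting index, worst nausea and rescue doses share the defect.** Section H names only ESAS and FLIE as examples and does not assign those outcomes to this test.

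**Conclusion.** The point holds in a limited form. For ESAS and FLIE the plan names a between-arm rank test with no baseline adjustment, scale, day or between-arm estimate, although the enrolment scores are there to be used. The loss of power relative to a baseline-adjusted analysis is about 10% at rho 0.2, 25% at 0.5 and 40% at 0.7. This assumes a 0.8 SD difference, roughly normal scores and 20 versus 10 patients; neither rho nor the difference comes from the documents. With low correlation or strong skew the gain from a plain linear model may be small or reversed, which a rank-based adjusted analysis addresses. The outcomes are supportive and exploratory, so the primary NRS estimate is not affected. The change is worth making because it costs little and produces the quantity that a later trial would need.

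**What to change.** Replace the Section H sentence, for these two instruments, with wording to this effect: FLIE and ESAS at day 15 (day 10 supportive) will be analysed with a linear model on arm, that outcome's own enrolment score and the NRS randomisation stratum (4–6 versus 7–10). The adjusted NEPA-minus-placebo difference will be reported with its 95% CI. Where scores are clearly skewed, the test will be a baseline-adjusted ANCOVA on ranks. The unadjusted Wilcoxon test will be kept as a check. All these results are exploratory, with no adjustment for multiplicity and no claim based on a single p-value.

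The linear model should not be extended to rescue-dose counts, for which it is poorly suited.

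The cost is SAP wording only, with no new visits, data or patients. The downsides are small: a linear-model assumption for bounded scores, covered by the rank-based version, and a baseline taken before the run-in, so the gain may be modest.
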